4.1 Inclusion Criteria

- 1. Men and women greater than 18 years of age
- 2. Subjects must be in good health based on medical history, physical examination, vital signs, and laboratory tests. In order to ensure sufficient enrollment of subjects in the higher age groups, volunteers with the following conditions may participate in the study:
 - a. Adequately controlled hypertension, with diastolic blood pressure ≤100 mmHg at screening.
 - b. Total cholesterol of ≤270 mg/dL
- 3. Body mass index (BMI) between 18 and 30 kg/m².

- 4. Has not used tobacco products, including smoking cessation nicotine-containing products (e.g., nicotine patch, nicotine gum), for at least the 3 months prior to screening.
- 5. Female subjects of child bearing potential must be using a medically acceptable method of contraception (oral contraception, Depo-Provera injection, IUD, condom with spermicide, diaphragm, cervical cap, progestin implant, abstinence, tubal ligation, oopherectomy, TAH) throughout the entire study period. All female subjects must consent to a serum and urine pregnancy test at screening and close-out and a urine pregnancy test just prior to the start of each treatment phase of the study, which must be negative at all time points.
- 6. All subjects must consent to a urine drug test at screening. Results must be negative. A positive result will be reported to the subject.
- 7. Does not consume more than 1 alcoholic beverage per day on average.
- 8. Able and willing to refrain from alcohol use within 48 hours prior to the first dose of study drug and during the study period until the final study visit.
- 9. Able to understand and comply with study procedures.
- 10. Able and willing to provide written informed consent prior to any study procedures being performed.

4.2 Exclusion Criteria

- 1. Female subjects who are pregnant or nursing a child.
- 2. Subjects who have received an investigational drug or used an experimental medical device within 30 days prior to screening, or who gave a blood donation of ≥ one pint within 8 weeks prior to screening.
- 3. Subjects with any coagulation, bleeding or blood disorders.
- 4. Subjects who are sensitive or allergic to celecoxib (Celebrex) or naproxen (Naprosyn) or their components.
- 5. Subjects who are sensitive or allergic to aspirin or other NSAIDs.
- 6. Subjects with documented history of any gastrointestinal disorders, including bleeding ulcers.
- History of significant cardiovascular disease (including stroke or TIA), renal, hepatic, respiratory (except infections which longer > 6 months prior to screening), immune, endocrine, hematopoietic disorder or neurological disorders.
- 8. History of cancer within the last 5 years (except for cutaneous basal cell or squamous cell cancer resolved by excision, or carcinoma in situ of the cervix adequately treated).
- 9. Has taken any prescription medication other than hormone replacement therapy (including males taking testosterone as a hormone replacement to treat a documented low testosterone level), thyroid replacement hormones, anti-hyperlipidemic agents, or anti-hypertensive medications. Individuals taking other/additional chronic stable medications can be considered on a case-by-case basis for inclusion in the study if agreed upon by judgment of the investigators.
- 10. Has taken the following NSAID or antisecretory agents within 2 weeks prior to study drug administration:
 - a. Nonsteroidal anti-inflammatory drugs (NSAIDs) including acetaminophen or other medications for pain, including aspirin or aspirin-containing products
 - b. Proton pump inhibitors, including Prilosec®, Prevacid®, Aciphex®, Protonix®, or Nexium® (antacid medications, including OTC products, are not permitted within 24 hours of dosing)
 - c. H₂ blockers, including Tagamet®, Zantac®, Axid®, or Pepcid®
- 11. Has ever taken the following anti-platelet or anti-coagulant agents:
 - a. Any anti-platelet agent, including Aggrenox®, Brilinta®, Plavix®, Ticlid®, Pletal®, ReoPro®, Integrilin®, Aggrastat®, Persantine®, or Effient®
 - b. Any anti-coagulant including Arixtra®, Coumadin®, acenocoumarol, Lovenox®, phenprocoumon, phenindione, heparin, Exanta®, Pradaxa®, argatroban, lepirudin, hirudin, bivalirudin, or Xarelto®
- 12. Used dietary or herbal supplements containing salicylates, Vitamin E, fish oil, or any other herbal supplements, within 14 days of study drug administration.

- 13. Subjects with any abnormal laboratory value or physical finding that according to the investigator may interfere with interpretation of the study results, be indicative of an underlying disease state, or compromise the safety of a potential subject.
- 14. Subjects who have had a history of drug or alcohol abuse within the last 6 months.
- 15. Subjects who are unwilling to provide a blood sample for genetic analyses and creation of a lymphoblastoid cell line.

4.3 Subject Recruitment and Screening

Healthy volunteers will be recruited from the database of healthy volunteers at the Institute for Translational Medicine and Therapeutics (ITMAT), through flyer, and by word of mouth.

Prior to enrollment, all volunteers will be asked to complete an online screening questionnaire to determine their eligibility. The screening questionnaire was prepared using Redcap, an on-line research electronic data capturing software. Volunteers will be sent an invitation email through RedCap with instructions to complete the questionnaire and a link. They will also have the option to complete the questionnaire over the phone by contacting the clinical study coordinator. The screening questionnaire can be accessed at https://redcap.med.upenn.edu/surveys/?s=FWCDYTXTE3.

Volunteers who meet inclusion criteria based on the screening questionnaire will undergo a screening visit, during which a complete medical history, physical examination, hematology and blood chemistries, urinalysis, urine drug test and urine pregnancy test (female subjects only) will be obtained.

4.4 Early Withdrawal of Subjects

4.4.1 When and How to Withdraw Subjects

All subjects are free to withdraw from participation in this study at any time, for any reason, and without prejudice.

The Investigator may terminate a subject from the study at any time for intolerable or unacceptable AEs, intercurrent illness, noncompliance with protocol requirements, administrative reasons, or in the Investigator's opinion to protect the subject's best interest.

If a subject is withdrawn before completing the study, the reason for withdrawal will be entered on the appropriate case report form (CRF). Whenever possible and reasonable, the evaluations which were to be conducted at the completion of the study should be performed at the time of premature discontinuation.

4.4.2 Data Collection and Follow-up for Withdrawn Subjects

Whenever possible and reasonable, the evaluations which were to be conducted at the completion of the study should be performed at the time of premature discontinuation. To encourage subjects to participate in the end-of-study clinic visit, up to 10 contacts will be initiated via e-mail, text message or phone by study coordinators. If this fails to motivate the subject, up to 2 phone calls will be initiated by the PI, Co-PI, or qualified sub-investigator (MD) in order to schedule the exit visit.

5 Study Drug

5.1 Description

Celecoxib and naproxen are FDA approved medications for pain and inflammatory diseases. The study drugs will be all administered at FDA approved therapeutic doses.

Celecoxib is a prescription drug that will be administered as commercially available 100 mg (low dose group) and 200 mg (high dose group) capsules. Naproxen is a prescription drug that will be administered as commercially available 250 mg (low dose group) and 500 mg (high dose group) tablets.

5.2 Treatment Regimen

During each treatment phase, subjects will receive celecoxib, naproxen, or placebo for 7 days. Subjects will be assigned to either a high dose arm (celecoxib 200 mg BID, naproxen 500 mg BID, or placebo) or a low dose arm (celecoxib 100 mg BID, naproxen 250 mg BID, or placebo). Subjects will be instructed to take the study medications twice a day (at approximately 8 AM and 8 PM) on an empty stomach with a full glass of water.

5.3 Method for Assigning Subjects to Treatment Groups

Subjects will be assigned alternately to the low dose or high dose treatment arm in blocks of 36 subjects (i.e. subjects 1-36 will be assigned to the low dose arm; subjects 37-72 will be assigned to the high dose arm, etc).

The order of administration of the three study drugs will be randomized. The independent study statistician will prepare randomization lists according to this schedule which will be sent to the investigational pharmacist (UPENN Investigational Drug Service). When notified that a subject has completed the screening period and is ready to begin treatment, the investigational pharmacist will select the next randomization label in sequence and dispense the assigned study treatment for that subject.

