3.1 General Design

The study is a double-blind, placebo-controlled trial investigating the pharmacologic response to celecoxib and naproxen in healthy adults. Subjects will be assigned to one of two treatment arms: a low dose arm and a high dose arm. Each treatment phase will be 7 days followed by a 3 day post-treatment assessment and a 2 week wash-out period. The order of the three treatment phases (celecoxib, naproxen, and placebo) will be randomized. The study schema is shown in the figure below:

Qualified subjects will have approximately 9 weeks of participation in this study (1 week/treatment phase x 3 treatment phases + 3 days/post-treatment assessment x 3 post-treatment assessments + 2 weeks/washout phase x 2 washout phases).

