5.4 Preparation and Administration of Study Drug

Study drug will be maintained and dispensed by the Investigational Drug Service (IDS) of the University of Pennsylvania ([name], contact person: [name] Jr., [contact] / [contact]). Commercially sourced celecoxib and naproxen will be blinded by IDS to match the placebo by over-encapsulation. As noted in section 5.7 (Packaging), the IDS will prepare blister packs of blinded study drug. The study drugs will be administered orally.

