5.8 Blinding of Study Drug

Blinding of the study drugs will be done by over-encapsulation at the Investigational Drug Service. All subjects and research staff will be blinded as to the sequence of study medications until the subject has completed the study. Codes linking randomization number for each subject to actual treatment will be secured in a sealed, opaque envelope and maintained in a locked drawer in the IDS. Research subjects will be given the emergency contact number for the study during the consenting process (see Attachment 2)

See section 8.4 (Unblinding Procedures) for a description of the process for unblinding a study subject.

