7.1 Sample Size Determination

144 subjects per treatment arm (low dose and high dose; total N=288) will be studied to compare the variability in COX-1 and COX-2 activity as the primary outcome in measurements on 12 individuals per group. These groups are 3 DRUGs (placebo, celecoxib, naproxen) via randomization, 2 DOSEs (high and low) via randomization, 2 SEXes (female: male = 1:1), 3 AGE groups (18y to 40y, 41y to 60y, 61y to 85y = 1:1:1), and 2 RACEs (African American, Caucasian = 1:1). Importantly, individuals from ethnicities or races other than African American and Caucasian will be invited to participate in the study; however, there will not be specific sample size targets in the other groups. We expect that less than 10% of the population will be Hispanic or Asian or belong to another race. Thus, we will explore the outcomes in these groups, but will not have the statistical power for formal primary analyses.

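### Section 7.1 says dose is randomized, but section 5.3 fixes the dose arm by subject number in alternating runs of 36, so low-versus-high contrasts would not be randomized if 5.3 is followed

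*Combined protocol and SAP*

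**What the plan says.** Section 5.3 gives the dose rule with a worked example: "subjects 1-36 will be assigned to the low dose arm; subjects 37-72 will be assigned to the high dose arm, etc". The next paragraph randomizes the order of the three study drugs and adds "The independent study statistician will prepare randomization lists according to this schedule". The pharmacist then takes the next label in sequence.

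Section 3.1 agrees about what is left to chance: "The order of the three treatment phases (celecoxib, naproxen, and placebo) will be randomized". Section 5.2 says only "Subjects will be assigned to either a high dose arm", with no mechanism.

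Section 7.1 builds the groups of 12 from drug, dose, sex, age and race, and describes dose as "2 DOSEs (high and low) via randomization". Section 7.2 sizes the study on a ratio of standard deviations between two such groups. It offers paired comparisons only between treatments within a dose group.

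On blinding, section 5.4 says "Commercially sourced celecoxib and naproxen will be blinded by IDS to match the placebo by over-encapsulation". Section 5.8 blinds subjects and staff to the sequence of medications and adds "Codes linking randomization number for each subject to actual treatment will be secured in a sealed, opaque envelope".

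**The concern.** The two descriptions of dose allocation cannot both be true. The runs of 36 cannot be read as permuted blocks, because the worked example gives a whole run one dose.

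Three things follow if 5.3 is what is done:

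- A reader of 7.1 would report low-versus-high contrasts as randomized when they are not.
- Staff at this single center who know 5.3 and the running count know the next subject's arm. Enrolment leaves room for judgment, such as the case-by-case decisions on other chronic medications in section 4.2, so selection by arm is possible.
- Dose tracks enrolment period, and with it anything that drifts over time, such as recruitment mix or assay conditions.

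**Working it through.** **1. The plan's own figure.** Inputs from 7.2: n=12 per group (11 and 11 df), two-sided 0.05, 80% power, SD 41.2. Solving P(F > F0.975/r²) + P(F < F0.025/r²) = 0.80 gives r = 2.42. Then 41.2 × 2.42 = 99.7. The 95% interval 41.2 × √(11/χ²) runs from 29.2 to 70.0. All agree with 7.2. Cells: 2 sexes × 3 ages × 2 races × 12 = 144 per dose, and × 2 = 288. None of this depends on how dose is allocated.

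**2. What 5.3 produces.** 288/36 = 8 runs, four low and four high, so 144:144 is reached with no chance step.
- Low-run midpoints: 18.5, 90.5, 162.5, 234.5; mean 126.5.
- High-run midpoints: 54.5, 126.5, 198.5, 270.5; mean 162.5.
- Difference: 36 positions, and 36/288 = 12.5% of accrual. If accrual were even over the 3-year study duration (an assumption), that is 0.125 × 36 months = 4.5 months.

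**3. Effect on the SD-ratio test of 7.2.** Simulated with 20,000 trials, total SD 1 and 3 subjects per run in each group of 12 (assumed). Type I error is 5.0% and 4.8% when runs shift the mean with an assumed intraclass correlation (ICC) of 0.02 and 0.05. It reaches about 5.6% only if the spread itself varies by run (assumed SD of log SD 0.1).

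**4. Effect on a contrast of means (illustration; the plan specifies no such test).** An ordinary 144 v 144 t-test of raw values has design effect 1 + 35 × ICC.

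| Assumed ICC | Design effect | Type I error |
|---|---|---|
| 0 | 1.00 | 5% |
| 0.02 | 1.70 | 13.3% |
| 0.05 | 2.75 | 23.7% |

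**5. Does change from own placebo cure this?** Only if a run's effect is the same in a subject's drug and placebo phases and so cancels; the error is then about 5%. Suppose instead that run shifts the change itself with variance v. With within-subject correlation 0.5, the change has SD √(2(1 − 0.5)) = 1, and the variance of the mean difference is understated by a factor of about (1 + 36v)/(1 + v).

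| Assumed v | Factor | Type I error |
|---|---|---|
| 0.01 | 1.35 | 9% |
| 0.02 | 1.69 | 13% |
| 0.05 | 2.67 | 23% |

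Comparing 4 v 4 run means (6 df), the simple form of a random run effect, restores 4.8% to 5.2% in 20,000 simulated trials for v from 0 to 0.05.

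**6. Power cost of that protection.** Detectable difference in means at 80% power, in SD units of a single measurement:
- Raw values: 0.33 for the ordinary test. With 4 v 4 run means, whose variance is ICC + (1 − ICC)/36, it is 0.40, 0.52 and 0.66 at ICC 0, 0.02 and 0.05.
- Change from own placebo, if the run effect cancels: 0.39, 0.33 and 0.26 for the ordinary test at assumed correlations 0.3, 0.5 and 0.7. With run means on 6 df it is 0.47, 0.40 and 0.31.

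**The case against.** The strongest reply is that this is a wording slip with little effect on the planned analysis. Much of that stands. No objective in section 2 names a dose contrast. The SD-ratio test keeps close to its nominal level. Eight alternating runs already hold the drift to 36 positions. Sex, age and race are non-randomized factors too. The demographic targets of 7.1, if met, balance that mix between arms, every subject has a placebo phase against which run differences can be checked, and the primary endpoints are laboratory assays. What does not stand is leaving both statements in place: dose, unlike sex or race, is claimed to be randomized.

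A reader might also infer more than the documents support:

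- **That the trial as a whole is not randomized.** Drug order is randomized, and the drug comparisons are within subject.
- **That the blind is broken.** Section 5.8 states blinding to sequence and seals the treatment codes, and the drugs are over-encapsulated. The arm can be inferred from the subject number, but no section says explicitly that the arm is hidden.
- **That type I error is 13% to 24%.** That figure belongs to a test of raw means that the plan does not contain, at assumed ICCs.
- **That dose was in fact allocated in runs.** The documents do not show which rule was used.

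**Conclusion.** The contradiction is real and rests on the text alone. If 5.3 is followed, low-versus-high contrasts are non-randomized, the arm is predictable from the subject number, and enrolment position differs by 36 places on average. The sample size and the 2.42 ratio stand.

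The consequence is modest: a false description of one design factor, and exposure of any dose contrast to period and selection effects. The size of the period effect cannot be taken from the documents; every error rate above depends on an assumed run effect, and at zero run effect there is no inflation from that source. The point should be fixed because the correction is cheap, but it does not undermine the trial's main comparisons.

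**What to change.** Reconcile 5.3 and 7.1 by one of two routes.

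**If the runs are kept or have already been used:**
- Remove the randomization claim for dose in 7.1 and label low-versus-high contrasts, in SDs or in means, as non-randomized.
- Commit any dose contrast in means to change from own placebo or baseline; 7.2 at present only permits change from baseline.
- Include run as a random effect in that analysis as well as in any analysis of raw means, because the change score removes a run effect only when it is the same in both phases.
- Do not fit run as a fixed effect when estimating the dose main effect. Each run has one dose, so run is nested in dose and the fixed terms would absorb the dose effect. The within-subject drug contrasts are not harmed by such a term.

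The cost is wording, plus lower power for dose contrasts in means (for raw values, 0.40 to 0.66 SD detectable instead of 0.33).

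**If dose is meant to be randomized and enrolment allows:** replace the runs in 5.3 with one concealed list, held by the pharmacy, that randomizes dose together with drug order. For example, use permuted blocks of 12 (2 doses × 6 orders); 288/12 = 24 blocks give 144:144 with N unchanged. State in 5.8 whether the dose arm is blinded. The cost is a new list, an amendment, and kits for both doses held at once.

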7.2 Statistical Methods

The primary hypothesis of this study is that one or more clinical, genetic, and environmental factor affects variability in COX-1 and COX-2 activity following placebo and NSAID treatment. Calculations may involve change from baseline or a summary of longitudinal measures such as the area under the curve, but for simplicity of illustration we describe only a single post-treatment value. For 80% power and a two-sided significance level of 0.05, with n=12 per group we can detect a ratio of standard deviations of 2.42 (calculated based on the F-distribution for the ratio of variances). For example, analysis of the data from our prior study¹⁵ provides an estimate of inter-subject standard deviation of 41.2; thus we could in this metric have adequate power to identify a standard deviation of 99.7. A 95% confidence interval on an estimated standard deviation of 41.2 with n=12 would range from approximately 29.2 to 70.0. For the paired comparisons between treatments within a dose group, the detectable ratio in standard deviations (and width of a confidence interval) will be smaller.

Exploratory transcriptomic, proteomic, and metabolomics analyses will be conducted by PENTACON collaborators using a variety of modelling techniques, such as Bayesian networks and ODE modelling. Microbiome analyses will utilize weighted and unweighted UniFrac, as well as measures of alpha diversity such as the Chao1 and Shannon Indices, to characterize communities.

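### The stated 80% power rests on 12 people in each dose x sex x age x race cell, but dose is assigned by enrolment number with no stratification or quota, so that cell size is not ensured.

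*Combined protocol and SAP*

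**What the plan says.** Section 7.1 plans 144 people in each dose arm, 288 in all, with variability in COX-1 and COX-2 activity "as the primary outcome in measurements on 12 individuals per group". The groups cross drug, dose, sex, three age bands and two races. Sex, age and race targets are given as ratios (1:1, 1:1:1 and 1:1).

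Section 7.2 attaches the power statement to that group size: "For 80% power and a two-sided significance level of 0.05, with n=12 per group we can detect a ratio of standard deviations of 2.42". The method named there is an F test comparing two variances.

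Section 5.3 is the only place that says how a person comes to a dose arm. It works by enrolment number: "subjects 1-36 will be assigned to the low dose arm; subjects 37-72 will be assigned to the high dose arm", and so on. Once a person is ready to start, "the investigational pharmacist will select the next randomization label in sequence and dispense the assigned study treatment for that subject". Sex, age and race are not mentioned there. Section 4.3, on recruitment and screening, gives no quota or cap either.

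**The concern.** The sample size depends on a joint balance: every sex x age x race stratum has to divide equally between the two doses. The ratios in 7.1 do not by themselves fix the 12 joint strata, and the rule in 5.3 takes no account of stratum. Applied as written, it leaves the cell sizes to the order in which people happen to enrol.

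This matters because the primary hypothesis in 7.2 is that clinical, genetic or environmental factors affect variability, and the power statement is about comparing standard deviations between groups of 12. If some cells are well below 12, comparisons involving them have less than the stated power. Balance of this kind cannot be restored once enrolment is complete.

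A separate inconsistency should be reconciled on its own account: 7.1 describes dose as randomised, while 5.3 alternates it. Simple randomisation of dose would remove that inconsistency and still leave the cell sizes uncontrolled.

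**Working it through.** **Inputs from the documents.** N = 288, with 144 per dose; 2 doses, 2 sexes, 3 age bands, 2 races; 12 per group (7.1). Two-sided alpha 0.05, 80% power, SD ratio 2.42, F test, reference SD 41.2 (7.2). Runs of 36 (5.3).

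**Cell count.** 2 x 2 x 3 x 2 = 24 cells, and 24 x 12 = 288. Drug is crossed within subject and adds no people.

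**Step 1: reproduce the plan's figures.** For group sizes n1 and n2, with the SD of group 1 equal to r times that of group 2, power is P(F > F0.975 / r²) + P(F < F0.025 / r²), where F has n1 − 1 and n2 − 1 degrees of freedom.
- At 12 v 12 (11 and 11 df) and r = 2.42, power is 80.0%. The ratio giving exactly 80% is 2.4196, which rounds to 2.42.
- 41.2 x 2.42 = 99.7, as stated ("adequate power to identify a standard deviation of 99.7").
- The chi-square interval for an SD of 41.2 at n = 12 is 29.2 to 70.0, as stated.

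The plan's arithmetic is right for n = 12. The question is whether n will be 12.

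**Step 2: cell sizes under the rule in 5.3.** Two assumptions, neither given in the documents: each of the 12 strata reaches 24 study-wide (288 / 12), and arrival order is unrelated to stratum. The low-dose count in a stratum is then hypergeometric: 24 people from 288, of whom 144 get low dose.
- Mean = 24 x 144/288 = 12.
- SD = sqrt(24 x 0.5 x 0.5 x 264/287) = 2.35.
- P(a given stratum splits 12:12) = 16.8%.
- P(all 24 cells are exactly 12) = C(24,12)^12 / C(288,144) = 6.5 x 10⁻⁹.
- P(a cell has 9 or fewer) = 0.143, so 24 x 0.143 = 3.4 cells on average.
- By simulation of 100,000 splits, the smallest cell averages about 7.5 and the largest about 16.5. The middle 95% of cells lie between 7 and 17.

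**Step 3: power at r = 2.42 with those cells.**

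| Contrast | Mean power | 95% range |
|---|---|---|
| Two strata at the same dose | 77.7% | 58.7% to 89.0% |
| High v low dose within a stratum | 77.5% | 60.4% to 80.5% |

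Within a stratum of 24 the two dose cells sum to 24, so a small cell always faces a large one:

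| Split | Larger SD in the bigger cell | Larger SD in the smaller cell |
|---|---|---|
| 16 v 8 | 67.7% | 77.5% |
| 17 v 7 | 60.4% | 74.8% |

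**Step 4: detectable ratio at 80% power for equal cells.**

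| Cells | Detectable ratio | Power at 2.42 |
|---|---|---|
| 12 v 12 | 2.42 | 80.0% |
| 10 v 10 | 2.68 | 70.7% |
| 9 v 9 | 2.87 | 64.8% |
| 8 v 8 | 3.12 | 58.1% |

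**Step 5: pooled contrasts.** Sex within one dose arm compares about 72 with 72 (144 / 2). The detectable ratio there is 1.40, and it stays between 1.40 and 1.41 if the split is 62 v 82.

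**The case against.** The strongest reply is that 12 per cell is itself the recruitment target. Section 7.1 speaks of 144 people per arm and lists dose among the group factors; read that way, meeting the target gives 12 per cell by definition. The run length fits, since 36 = 12 strata x 3 and four runs per dose give 4 x 3 = 12. Volunteers are screened before the pharmacist is notified (4.3 and 5.3), so staff could fill each run by quota without any change to how labels are drawn. This much stands: the documents do not exclude such a quota. A reader might infer that cells of 12 cannot occur under this plan, and the documents do not support that. They do not state a quota either, and the study is not bound by one that is unwritten.

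A second tempting reading is that power generally drops to the 58% found at 8 v 8. It does not. With 24 per stratum, a within-stratum dose contrast cannot be 8 v 8, because an 8-person cell faces 16. For two strata at the same dose, both cells are 8 or fewer in only about 0.3% of pairs.

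Third, the cell-by-cell comparison in 7.2 is offered as an illustration. Pooled contrasts hardly depend on cell balance, and drug comparisons are made within subject, where 7.2 expects a smaller detectable ratio. That also stands, and it limits the reach of the point. It does not rescue the stated 2.42, which is tied explicitly to 12 per group.

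**Conclusion.** The point holds in a limited form. The plan's power figure is correct for 12 v 12, but no stated procedure produces cells of 12. If strata fill to 24 study-wide and arrival order is unrelated to stratum, mean power at a ratio of 2.42 is about 77.5-78% instead of 80.0%. Around 3 of the 24 cells would hold 9 or fewer, and individual contrasts could fall to about 60% (for example 17 v 7 with the larger SD in the 17). If arrivals cluster in time by stratum, runs of 36 could make the imbalance larger; the documents give no arrival rates, so no figure can be put on that. If an unwritten quota is in fact used, the loss disappears and only the wording needs correcting. The change should be made because it is cheap beforehand and impossible afterwards; the expected loss does not threaten the trial.

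**What to change.** Adopt one of the first two options in 5.3; the third is a fallback.

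1. Allocate dose 1:1 in permuted blocks within each of the 12 sex x age x race strata, with a cap of 24 per stratum. When the strata are full, every cell is 12 and power at 2.42 is 80.0%. Cost: 12 short lists at the pharmacy and a change of wording.
2. Keep the runs of 36 and require exactly 3 people per stratum in each run. Four runs per dose then give 12 per cell. Cost: one sentence, but a slowly recruiting stratum may delay the closing of a run.
3. If neither is done, state in 7.2 that 2.42 applies only at 12 v 12, and give the detectable ratio over the cell sizes expected, for example 2.68 at 10 v 10 and 3.12 at 8 v 8. Cost: wording only, but the imbalance remains.

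Under options 1 and 2, 7.1 should also say whether people of other races or ethnicities count within the 288, since they belong to none of the 12 strata.
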